2. ABBREVIATIONS

Abbreviations pertain to the Statistical Analysis Plan (SAP) only (not the tables, figures and listings [TFLs]).

AE	Adverse event
ALP	Alkaline phosphatase
ALT	Alanine aminotransferase
AUC	Area under the concentration versus time curve
AUC(0-t _{last})	Area under the concentration versus time curve from time zero to time t, where t is the last time point with a measurable concentration
AUC(0-∞)	Area under the concentration versus time curve from time zero to infinity
AUC(0-168h)	Area under the concentration versus time curve from time zero to 168 hours post dose
AUC(0-336h)	Area under the concentration versus time curve from time zero to 336 hours post dose
AUC(0-t _{last})	Area under the concentration versus time curve from time zero to time t, where t is the last time point with a measurable concentration
%AUC(t _{last} -∞)	Percentage of AUC(0-∞) extrapolated
BQL	Below the quantifiable lower limit of the assay
C _{max}	Maximum observed drug concentration
CI	Confidence interval
CL/F	Apparent total body clearance of drug calculated after extra-vascular administration
CRF	Case Report Form
CRU	Clinical research unit
CSR	Clinical Study Report
CV	Coefficient of variation
EC	Early Clinical
ECG	Electrocardiogram
e.g.	For example (Latin: exempli gratia)
ICH	International Council on Harmonisation
LLOQ	Lower limit of quantitation
LS	Least square

MedDRA	Medical Dictionary for Regulatory Activities
MRE	Magnetic resonance elastography
NA	Not applicable
PK	Pharmacokinetic
PFS	Prefilled syringe
SAP	Statistical Analysis Plan
SC	Subcutaneous
SD	Standard deviation
SDP	Single dose pen
SOP	Standard Operating Procedure
TBL	Total bilirubin
TFLs	Tables, Figures, and Listings
$t_{1/2}$	Half-life associated with the terminal rate constant (λ_z) in non-compartmental analysis
t_{max}	Time of maximum observed drug concentration
ULN	Upper limit of normal
V_{ss}/F	Apparent volume of distribution at steady state after extra-vascular administration
V_z/F	Apparent volume of distribution during the terminal phase after extra-vascular administration
WHO	World Health Organization

3. INTRODUCTION

This SAP has been developed after review of the Clinical Study Protocol (final version dated 24 September 2017).

This SAP describes the planned analysis of the safety, tolerability and pharmacokinetic (PK) data from this study. A detailed description of the planned TFLs to be presented in the clinical study report (CSR) is provided in the accompanying TFL shell document.

The intent of this document is to provide guidance for the statistical and PK analyses of data. In general, the analyses are based on information from the protocol, unless they have been modified by agreement between Eli Lilly and Company and Covance Early Clinical (EC) Biometrics. A limited amount of information concerning this study (e.g., objectives, study design) is given to help the reader's interpretation. This SAP must be signed off prior to first subject administration for this study. When the SAP and TFL shells are agreed upon and finalized, they will serve as the template for this study's CSR.

This SAP supersedes the statistical considerations identified in the protocol; where considerations are substantially different, they will be so identified. If additional analyses are required to supplement the planned analyses described in this SAP, they may be performed and will be identified in the CSR. Any substantial deviations from this SAP will be agreed upon between Eli Lilly and Company and Covance EC Biometrics and identified in the CSR. Any minor deviations from the TFLs may not be documented in the CSR.

This SAP is written with consideration of the recommendations outlined in the International Council on Harmonisation (ICH) E9 Guideline entitled Guidance for Industry: Statistical Principles for Clinical Trials¹ and the ICH E3 Guideline entitled Guidance for Industry: Structure and Content of Clinical Study Reports².

4. STUDY OBJECTIVES

4.1 Primary Objective

- To evaluate the relative bioavailability of a single dose of dulaglutide administered subcutaneously (SC) to healthy subjects as a single injection by single dose pen (SDP; test) compared to 3 injections by prefilled syringe (PFS; reference).

4.2 Secondary Objective

- To assess the tolerability of a single dose of dulaglutide administered SC to healthy subjects as a single injection by SDP compared to 3 injections by PFS.

5. STUDY DESIGN

This study is a Phase 1, single-center, open-label, randomized, 2-period, crossover study in healthy subjects to evaluate the relative bioavailability of 4.5 mg of a new formulation of

dulaglutide administered SC as a single injection by SDP (test) compared to 3 injections by PFS (reference).

Each subject will provide informed consent for study participation and will undergo a screening examination within 27 days prior to enrollment.

In each treatment period, subjects will be admitted to the clinical research unit (CRU) on Day -1. On Day 1 of each period, subjects will receive a single dose of 4.5 mg dulaglutide administered SC as a single SDP injection or as 3 injections by PFS according to the randomization schedule. Blood samples will be collected predose and up to 336 hours postdose to measure dulaglutide concentrations. At a minimum, subjects will remain at the CRU until collection of the 168-hour (Day 8) PK sample in each period.

There will be a washout period of at least 28 days between doses in Periods 1 and 2. Each subject will be required to return to the CRU for a follow-up visit 28 ± 3 days after the last dulaglutide dose. The total duration for each subject (from screening through the follow-up visit) is approximately 84 days. The treatment sequences are detailed below:

Treatment Sequence	Period 1	Period 2
1	Prefilled Syringe	Single Dose Pen
2	Single Dose Pen	Prefilled Syringe

Safety and tolerability will be assessed throughout the study by means of vital sign measurement, physical examination, clinical laboratory tests, electrocardiograms (ECGs), and AE recording.

6. TREATMENTS

The following is a list of the study treatment abbreviations that will be used in the TFLs.

Study Treatment Name	Abbreviation	Treatment order in TFL
4.5 mg Dulaglutide (Prefilled Syringe)	Dulaglutide (PFS)	1
4.5 mg Dulaglutide (Single Dose Pen)	Dulaglutide (SDP)	2

7. SAMPLE SIZE JUSTIFICATION

Approximately 24 subjects may be enrolled in order that at least 18 subjects complete the study. The sample size was based on a within-subject variability (coefficient of variation) of 21% for the area under the concentration versus time curve (AUC) and maximum observed drug concentration (C_{max}) of dulaglutide from previous studies. Eighteen subjects will provide a 90%

probability that the half-width of the 90% confidence interval (CI) of the ratio of the geometric means for AUC and C_{\max} is no larger than 14%.

Subjects who are randomized may be replaced to ensure that at least 18 subjects may complete the study.

8. DEFINITION OF ANALYSIS POPULATIONS

The “Safety” population will consist of all enrolled subjects, whether or not they completed all protocol requirements.

The “Pharmacokinetic” population will consist of all subjects who received at least one dose of dulaglutide and have evaluable PK data.

All protocol deviations that occur during the study will be considered for their severity/impact and will be taken into consideration when subjects are assigned to analysis populations.

9. STATISTICAL METHODOLOGY

9.1 General

Data listings will be provided for all data that is databased. Summary statistics and statistical analysis will only be presented for data where detailed in this SAP. For continuous data, summary statistics will include the arithmetic mean, arithmetic standard deviation (SD), median, min, max and N; for log-normal data (e.g. the PK parameters: AUCs and C_{\max}) the geometric mean and geometric coefficient of variation (CV%) will also be presented. For categorical data, frequency count and percentages will be presented. Data listings will be provided for all subjects up to the point of withdrawal, with any subjects excluded from the relevant population highlighted. Summary statistics and statistical analyses will generally only be performed for subjects included in the relevant analysis population. For the calculation of summary statistics and statistical analysis, unrounded data will be used.

Mean change from baseline is the mean of all individual subjects’ change from baseline values. Each individual change from baseline will be calculated by subtracting the individual subject’s baseline value from the value at the timepoint. The individual subject’s change from baseline values will be used to calculate the mean change from baseline using a SAS procedure such as Proc Univariate.

Data analysis will be performed using SAS[®] Version 9.4 or greater.

9.2 Demographics and Subject Disposition

Subject disposition will be listed. The demographic variables age, sex, race, ethnicity, body weight, height and body mass index will be summarized and listed. Tobacco/nicotine habits will be listed.

9.3 Pharmacokinetic Assessment

9.3.1 Pharmacokinetic Analysis

Pharmacokinetic parameter estimates will be determined using non-compartmental procedures in validated software program (Phoenix WinNonlin Version 6.4 or later).

Plasma concentrations of dulaglutide will be used to determine the following PK parameters, when possible:

Parameter	Units	Definition
AUC(0-∞)	ng.h/mL	area under the concentration versus time curve from time zero to infinity
AUC(0-168h)	ng.h/mL	area under the concentration versus time curve from time zero to 168 hours post dose
AUC(0-336h)	ng.h/mL	area under the concentration versus time curve from time zero to 336 hours post dose
AUC(0-t _{last})	ng.h/mL	area under the concentration versus time curve from time zero to time t, where t is the last time point with a measurable concentration
%AUC(t _{last} -∞)	%	percentage of AUC(0-∞) extrapolated
C _{max}	ng/mL	maximum observed drug concentration
t _{max}	h	time of maximum observed drug concentration
t _½	h	half-life associated with the terminal rate constant (λ_z) in non-compartmental analysis
CL/F	L/h	apparent total body clearance of drug calculated after extra-vascular administration
V _z /F	L	apparent volume of distribution during the terminal phase after extra-vascular administration
V _{ss} /F	L	apparent volume of distribution at steady state after extra-vascular administration

Additional PK parameters may be calculated, as appropriate. The software and version used for the final analyses will be specified in the clinical study report. Any exceptions or special handling of data will be clearly documented within the final study report.

Formatting of tables, figures and abbreviations will follow the Eli Lilly Global PK/PD/TS Tool: NON-COMPARTMENTAL PHARMACOKINETIC STYLE GUIDE. The version of the tool effective at the time of PK analysis will be followed.

General PK Parameter Rules

- Actual sampling times will be used in the final analyses of individual PK parameters, except for non-bolus pre-dose sampling times which will be set to zero.

- C_{\max} and t_{\max} will be reported from observed values. If C_{\max} occurs at more than one time point, t_{\max} will be assigned to the first occurrence of C_{\max} .
- AUC parameters will be calculated using a combination of the linear and logarithmic trapezoidal methods (linear-log trapezoidal rule). The linear trapezoidal method will be applied up to t_{\max} and then the logarithmic trapezoidal method will be used after t_{\max} . The minimum requirement for the calculation of AUC will be the inclusion of at least three consecutive plasma concentrations above the lower limit of quantification (LLOQ), with at least one of these concentrations following C_{\max} . AUC(0- ∞) values where the percentage of the total area extrapolated is more than 20% will be flagged. Any AUC(0- ∞) value excluded from summary statistics will be noted in the footnote of the summary table.
- Half-life ($t_{1/2}$) will be calculated, when appropriate, based on the apparent terminal log-linear portion of the concentration-time curve. The start of the terminal elimination phase for each subject will be defined by visual inspection and generally will be the first point at which there is no systematic deviation from the log-linear decline in plasma concentrations. Half-life will only be calculated when a reliable estimate for this parameter can be obtained comprising of at least 3 data points. If $t_{1/2}$ is estimated over a time window of less than 2 half-lives, the values will be flagged in the data listings. Any $t_{1/2}$ value excluded from summary statistics will be documented in the footnote of the summary table.
- A uniform weighting scheme will be used in the regression analysis of the terminal log-linear portion of the concentration-time curve.
- The parameters based on observed C_{last} will be reported.

Individual PK Parameter Rules

- Only quantifiable concentrations will be used to calculate PK parameters with the exception of special handling of certain concentrations reported below the lower limit of quantitation (BQL). Plasma concentrations reported as BQL will be set to a value of zero when all of the following conditions are met:
 - The compound is non-endogenous.
 - The samples are from the initial dose period for a subject or from a subsequent dose period following a suitable wash-out period.
 - The time points occur before the first quantifiable concentration.
- All other BQL concentrations that do not meet the above criteria will be set to missing.
- Also, where two or more consecutive concentrations are BQL towards the end of a profile, the profile will be deemed to have terminated and therefore any further quantifiable concentrations will be set to missing for the calculation of the PK parameters unless it is considered to be a true characteristic of the profile of the drug.

Individual Concentration vs. Time Profiles

- Individual concentrations will be plotted utilizing actual sampling times.
- The terminal point selections will be indicated on a semi-logarithmic plot.

Average Concentration vs. Time Profiles

- The average concentration profiles will be graphed using scheduled (nominal) sampling times.
- The average concentration profiles will be graphed using arithmetic average concentrations.
- The pre-dose average concentration for single-dose data from non-endogenous compounds will be set to zero. Otherwise, only quantifiable concentrations will be used to calculate average concentrations.
- Concentrations at a sampling time exceeding the sampling time window specified in the protocol, or $\pm 10\%$, will be excluded from the average concentration profiles.
- Concentrations excluded from the mean calculation will be documented in the final study report.
- A concentration average will be plotted for a given sampling time only if 2/3 of the individual data at the time point have quantifiable measurements that are within the sampling time window specified in the protocol or $\pm 10\%$. An average concentration estimated with less than 2/3 but more than 3 data points may be displayed on the mean concentration plot if determined to be appropriate and will be documented within the final study report.

Treatment of Outliers during Pharmacokinetic Analysis

Application of this procedure to all pharmacokinetic analyses is not a requirement. Rather, this procedure provides justification for exclusion of data when scientifically appropriate. This procedure describes the methodology for identifying an individual value as an outlier for potential exclusion, but does not require that the value be excluded from analysis. The following methodology will not be used to exclude complete profiles from analysis.

Data within an Individual Profile

A value within an individual profile may be excluded from analysis if any of the following criteria are met:

- For pharmacokinetic profiles during single dosing of non-endogenous compounds, the concentration in a pre-dose sample is quantifiable.
- For any questionable datum that does not satisfy the above criteria, the profile will be evaluated and results reported with and without the suspected datum.

Data between Individual Profiles

1. If $n < 6$, then the dataset is too small to conduct a reliable range test. Data will be analyzed with and without the atypical value, and both sets of results will be reported.
2. If $n \geq 6$, then an objective outlier test will be used to compare the atypical value to other values included in that calculation:
 - a. Transform all values in the calculation to the logarithmic domain.
 - b. Find the most extreme value from the arithmetic mean of the log transformed values and exclude that value from the dataset.

- c. Calculate the lower and upper bounds of the range defined by the arithmetic mean $\pm 3 \times \text{SD}$ of the remaining log-transformed values.
- d. If the extreme value is within the range of arithmetic mean $\pm 3 \times \text{SD}$, then it is not an outlier and will be retained in the dataset.
- e. If the extreme value is outside the range of arithmetic mean $\pm 3 \times \text{SD}$, then it is an outlier and will be excluded from analysis.

If the remaining dataset contains another atypical datum suspected to be an outlier and $n \geq 6$ following the exclusion, then repeat step 2 above. This evaluation may be repeated as many times as necessary, excluding only one suspected outlier in each iteration, until all data remaining in the dataset fall within the range of arithmetic mean $\pm 3 \times \text{SD}$ of the log-transformed values.

Reporting of Excluded Values

Individual values excluded as outliers will be documented in the final report. Approval of the final report will connote approval of the exclusion.

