10.1. Sample Size Determination

Approximately 24 subjects may be enrolled in order that at least 18 subjects complete the study. The sample size was based on a within-subject variability (coefficient of variation) of 21% for AUC and C_{\max} of dulaglutide from previous studies. Eighteen subjects will provide a 90% probability that the half-width of the 90% confidence interval (CI) of the ratio of the geometric means for AUC and C_{\max} is no larger than 14%.

Subjects who are randomized may be replaced to ensure that at least 18 subjects may complete the study.

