9.3.2 Pharmacokinetic Statistical Methodology

The PK parameters will be summarized using descriptive statistics by treatment and also presented graphically. Mean (with and without SD bars) and individual profiles over time will be presented for PK concentrations.

The PK parameter estimates will be evaluated to determine the relative bioavailability of dulaglutide administered SC by SDP (test) compared to dulaglutide administered by PFS (reference).

Log-transformed C_{\max} and AUC(0- ∞) (primary parameters) and AUC(0-168h) and AUC(0-336h) (secondary parameters) will be evaluated in a linear mixed-effects analysis of variance model with fixed effects for treatment (SDP or PFS), period, and sequence and a random effect for subject within sequence. The ratios of least squares geometric means of SDP compared to PFS, as well as the corresponding 90% CIs, will be estimated and reported.

Example SAS code is given below:

```
proc mixed data=pk;  
class subject treatment period sequence;  
model log(pk) = treatment period sequence / ddfm=kr;  
lsmeans treatment / pdiff alpha=0.1;  
random intercept / subject=subject(sequence);  
run;
```

The t_{\max} will be analyzed nonparametrically using the Wilcoxon signed rank test. Estimates of the median difference and the corresponding 90% CIs will be calculated.

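### Could AUC(0-∞) values be dropped from the primary comparison without a stated rule?

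*SAP*

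**What the plan says.** Five places bear on this.

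- **SAP 9.3.1, extrapolation.** AUC(0-∞) "values where the percentage of the total area extrapolated is more than 20% will be flagged". No further action is attached to the flag. The next sentence says that any AUC(0-∞) "value excluded from summary statistics will be noted in the footnote of the summary table".
- **SAP 9.3.1, terminal slope.** "Half-life will only be calculated when a reliable estimate for this parameter can be obtained comprising of at least 3 data points". If the half-life "is estimated over a time window of less than 2 half-lives, the values will be flagged in the data listings". A footnote sentence like the one for AUC(0-∞) follows.
- **SAP 9.3.1, outliers between profiles.** With at least six values, the most extreme value is compared with the mean and SD of the remaining log values. "If the extreme value is outside the range of arithmetic mean" ± 3 SD, it is excluded from analysis and reported. The procedure's introduction makes its use optional.
- **SAP 8.** The PK population is "all subjects who received at least one dose of dulaglutide and have evaluable PK data". This is a rule about subjects, and evaluable is not defined.
- **SAP 9.3.2.** Log C_max and log AUC(0-∞), as primary parameters, and log AUC(0-168h) and AUC(0-336h), as secondary ones, "will be evaluated in a linear mixed-effects analysis of variance model with fixed effects for treatment (SDP or PFS), period, and sequence", with subject within sequence as a random effect. The section has no rule for flagged or excluded values.

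On precision, Protocol 10.1 and SAP 7 assume a within-subject CV of 21%. Protocol 10.1 states: "Eighteen subjects will provide a 90% probability that the half-width of the 90% confidence interval (CI) of the ratio of the geometric means" is at most 14%, on both primary parameters.

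**The concern.** AUC(0-∞) carries half of the primary comparison, and the SAP foresees that some of its values will be set aside. The footnote sentence gives no reason for exclusion: it could be the 20% flag, the 2-half-life flag or a slope judged unreliable. It also does not say when the decision is made or whether the value leaves the mixed model as well as the descriptive table. One could imagine one analyst fitting the model to all values and another fitting it to unflagged values only, each believing the plan was followed. The study is open-label, so such a choice could be made with treatment and results in view.

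At stake would be the precision that set the sample size. A crossover estimates the treatment contrast almost entirely from subjects with both periods, so each excluded value costs roughly one complete pair.

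**Working it through.** **1. The plan's own precision figure.** Inputs: CV 21%, 18 completers, 90% CI, 14% (Protocol 10.1, SAP 7).

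- σ_w = √ln(1 + 0.21²) = 0.2077.
- Log half-width at the true σ_w for n complete pairs: h = t(0.95, n−2) × σ_w × √(2/n). At n = 18: 1.746 × 0.2077 × 0.3333 = 0.1209.
- Probability that the half-width is within a limit L: P = F_χ²[(n−2)(L/h)²; n−2 df].
- Reading 14% as the lower side of the ratio, L = −ln 0.86 = 0.1508. At n = 18: 16 × (0.1508/0.1209)² = 24.9, so P = 92.8%. At n = 17, P = 88.9%. Eighteen is therefore the smallest n that reaches 90%, and the stated figure reproduces.
- Reading 14% on the log scale (L = 0.14), P at n = 18 is 83.8%. The 90% figure depends on the lower-side reading.

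**2. How likely flags are.** Inputs: half-life about 5 days and sampling to 336 h (Protocol 5.4). The documents give no t_max; 24, 48 and 72 h are assumed.

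- Simple exponential decline: 0.5^(336/120) = 14.4% extrapolated; 20% is reached at a half-life of 6.0 days.
- With first-order absorption, the share beyond T is (k_a e^(−kT) − k e^(−k_a T)) / (k_a − k), where k = ln 2/120 per hour and k_a is set to give the assumed t_max.

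| Assumed t_max | Extrapolated at 5-day half-life | Half-life at which 20% is crossed |
|---|---|---|
| 24 h | 15.0% | 5.9 days |
| 48 h | 16.2% | 5.7 days |
| 72 h | 18.2% | 5.3 days |

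- A terminal window of 96–336 h is 240 h, exactly 2 half-lives at 5 days, so the second flag is also close.

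A typical profile passes and a subject with a modestly longer half-life does not. How many are flagged depends on between-subject and assay variability, which the documents do not give. Simulations with assumed half-life CV of 10–30%, assay CV of 5–15% and t_max of 24–72 h put the share anywhere from 9% to 47%, so no single rate can be relied on.

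**3. Cost if flagged values were dropped from the model.** Lower-side reading, each excluded value counted as a lost pair:

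| Complete pairs | 18 | 17 | 16 | 14 | 11 |
|---|---|---|---|---|---|
| P(half-width ≤ 14%) | 92.8% | 88.9% | 83.6% | 69.5% | 44.2% |

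Eighteen is the minimum number of completers; about 24 may be enrolled. With 24 completers, P is 99.9%, and it is 98.7% at 21 pairs.

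**4. Whether the plan drops them.** Taking the text in order:

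- Above 20% extrapolated, the only action is a flag.
- The footnote sentence concerns summary statistics. SAP 9.1 treats summary statistics and statistical analysis as separate items, so exclusion from one does not imply exclusion from the other.
- SAP 9.3.2 says AUC(0-∞) goes into the model and makes no exception.
- The one value-level rule that speaks of exclusion from analysis is the outlier test. It has a numerical criterion and a reporting duty, and the footnote sentence can be read as the table-level record of such cases.
- If fewer than three usable terminal points exist, no half-life is calculated and no AUC(0-∞) can be formed. That is a missing value, not an excluded one.

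Fitting the model to unflagged values only would thus apply a rule the SAP does not contain. SAP 3 requires substantial deviations to be agreed and identified in the study report.

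**The case for a change.** The strongest case for a change is that silence is not a rule. The outlier test is optional and says nothing about extrapolation; a value with 25% extrapolated can sit well inside mean ± 3 SD. A footnote discloses a decision after it is made and does not fix it beforehand. Summary statistics could be used loosely, and some analysts do carry table exclusions into the model. The remedy would cost a sentence or two.

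Much of this stands. The gap in the text is real, reliable and evaluable are left to judgement, and flags are a realistic prospect. It would be too strong, though, to say that SAP 9.3.1 has no exclusion criterion at all.

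The step from gap to harm does not stand. It needs analysts to adopt a drop rule that appears nowhere, against the plain wording of SAP 9.3.2. Even then, the simulations behind the flag rates show the average treatment ratio shifting by 0.1% or less at t_max of 24–48 h and 0.6% at 72 h. The effect would be lost precision with little systematic bias, provided t_max is similar for the two devices. AUC(0-336h), which needs little or no extrapolation, goes through the same model, and C_max is also primary. A reader could see whether the AUC(0-∞) result rests on the tails.

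A related point is the sampling window. Protocol 5.1 and 5.4 and SAP 5 say up to 336 h. The Schedule of Activities adds a PK sample at follow-up, and Appendix 5 counts 19 samples (9 × 2 + 1). Whether that late sample enters the terminal slope is not stated. If it did, it would lengthen the profile in Period 2 only, for both sequences. Sequence sizes are planned to be about equal and the model has a period term, so the treatment contrast is protected from an average shift of that kind. This is a separate wording matter.

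**Conclusion.** No change is needed. The SAP leaves out a sentence that most analysts would supply in the same way: a flagged AUC(0-∞) value is annotated and stays in the primary model, and a value is absent only when the terminal slope cannot be estimated or the outlier procedure removes it. On that reading the analysis is sound and its precision is as designed, with a 92.8% probability of meeting 14% at 18 complete pairs.

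The loss that looked threatening (88.9% at 17 pairs, 69.5% at 14) is arithmetically correct but conditional. It rests on the lower-side reading of 14%, on exactly 18 completers, on flag rates driven by variabilities the documents do not give, and on an exclusion rule the plan does not state. An explicit sentence would be tidy, but it would only write down the default and would not alter the planned result.

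### The SAP's between-profile outlier test uses a fixed 3-SD limit for the most extreme value, so in about 18% of clean datasets at n = 18 to 24 a valid PK value qualifies for exclusion

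*SAP*

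**What the plan says.** SAP 9.3.1, under the heading on data between individual profiles, sets two rules by dataset size.

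- Below six values, "then the dataset is too small to conduct a reliable range test", and results are reported both with and without the atypical value.
- From six values up, "then an objective outlier test will be used to compare the atypical value to other values included in that calculation". On the log scale the analyst must "Find the most extreme value from the arithmetic mean of the log transformed values and exclude that value from the dataset". The next step begins "Calculate the lower and upper bounds of the range defined by the arithmetic mean", with a width of 3 SD of the remaining values. If the value falls outside, "then it is an outlier and will be excluded from analysis".

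The test can be iterated: "This evaluation may be repeated as many times as necessary, excluding only one suspected outlier in each iteration". The multiplier of 3 does not change with n.

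The introduction to the outlier procedure, in the same section, is permissive. It says "Application of this procedure to all pharmacokinetic analyses is not a requirement", and that the method identifies candidates but "does not require that the value be excluded from analysis". Excluded values are to be documented in the final report. The requirement to show both sets of results does not extend to between-profile exclusions at n of six or more.

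**The concern.** A 3-SD limit sounds strict because a single, preselected normal value rarely falls outside it. This test is different in two ways. The value is the largest of n deviations, so it had n chances to be far out. The SD is also taken after that value is removed, so it is smaller than the SD of the full set. Both features raise the chance that ordinary data fail the test, and the SAP gives no error rate for it.

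At stake is how much weight the test can bear as a reason for dropping C_max or AUC values from the primary comparison. The SAP presents it as an objective justification. If clean data meet the criterion often, meeting it says little about whether a value is aberrant. Removing true extremes also makes the reported spread too small.

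**Working it through.** **Inputs.** Limit, selection step and minimum n: SAP 9.3.1. Planned n of 18 to 24 and within-subject CV of 21%: SAP 7 and protocol 10.1. Between-subject variability is not given, so a range is assumed in step 4.

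**1. The plan's own figure.** The SAP states no false-exclusion rate. Its precision statement can be checked, which confirms the variability used below. The within-subject log SD is sqrt(ln(1 + 0.21²)) = 0.2077. With 18 subjects, the 90th percentile of the 90% CI half-width is

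t(0.95; 16) × 0.2077 × sqrt(χ²(0.90; 16)/16) × sqrt(2/18) = 1.746 × 0.2077 × sqrt(23.54/16) × 0.3333 = 0.1466 on the log scale.

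The lower side of the ratio is 1 − exp(−0.1466) = 13.6%, within the stated 14%. With 17 subjects it is 14.1%. The figure reproduces on the lower-side convention.

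**2. False-exclusion rate.** For normal log values, let D be the distance of one value from the mean of the others, divided by the SD of the others. Then D / sqrt(n/(n−1)) follows t with n−2 degrees of freedom. The chance that a given valid value lies beyond 3 SD is p = 2P(t(n−2) > 3/sqrt(n/(n−1))). The value farthest from the overall mean also has the largest D, so the test flags a dataset when any of the n values exceeds the limit. That probability is at most n × p.

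| n | 3/sqrt(n/(n−1)) | p per value | n × p | Simulated (400,000 datasets) |
|---|---|---|---|---|
| 6 | 2.739 | 0.0520 | 31.2% | 31.2% |
| 12 | 2.872 | 0.0166 | 19.9% | 19.9% |
| 18 | 2.915 | 0.0101 | 18.2% | 18.0% |
| 24 | 2.937 | 0.0076 | 18.3% | 18.1% |

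With the repeat rule, about 3% of clean datasets at n = 18 to 24 lose two or more values.

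**3. Effect on SDs.** The iterated rule was applied to 40,000 clean datasets per n and always obeyed. Averaged over all datasets, the log-scale SD is 0.955 of its full-data value at n = 18 and 0.964 at n = 24. Among datasets that lose a value, the ratios are 0.75 and 0.80.

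**4. Effect on the SDP/PFS 90% CI.** The rule was run on both treatments for one parameter and always obeyed. The CI came from complete pairs, adjusted for period (20,000 trials per row). Between-subject log SDs of 0.2, 0.3 and 0.5 are assumed; by sqrt(exp(s²) − 1) these are CVs of about 20%, 31% and 53%.

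| n | Between-subject log SD | Coverage, full data | Coverage, after rule | Loss (points, unrounded data) | Mean width ratio |
|---|---|---|---|---|---|
| 18 | 0.2 | 0.901 | 0.887 | 1.4 | 0.992 |
| 18 | 0.3 | 0.899 | 0.891 | 0.7 | 1.000 |
| 18 | 0.5 | 0.900 | 0.896 | 0.4 | 1.006 |
| 24 | 0.2 | 0.899 | 0.887 | 1.2 | 0.992 |
| 24 | 0.3 | 0.902 | 0.894 | 0.8 | 0.999 |
| 24 | 0.5 | 0.896 | 0.894 | 0.3 | 1.004 |

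A repeat run at CVs of 20%, 30% and 50% gave losses of 0.4 to 1.6 points. The loss is thus about 0.5 to 1.5 points. In these rows 29-33% of trials lose at least one value, and coverage within those trials is 86-89%.

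**5. A limit that holds its error rate.** Setting n × p equal to α gives k(n) = t(n−2; 1 − α/(2n)) × sqrt(n/(n−1)).

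- α = 5%: n = 18, 3.531 × 1.029 = 3.63; n = 24, 3.488 × 1.0215 = 3.56.
- α = 1%: n = 18, 4.296 × 1.029 = 4.42; n = 24, 4.152 × 1.0215 = 4.24.

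**The case against.** The strongest reply is that the procedure is discretionary. It is invoked for a value that already looks atypical, need not be applied, and need not lead to exclusion. A reader might infer from the rates above that the SAP deletes a valid value in 18% of clean datasets. The documents do not support that: 18% is the rate at which a valid value qualifies. This part of the reply stands. It does not rescue the limit, because the SAP offers the test as justification for exclusion, and step 2e, read alone, makes exclusion mandatory.

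A second reply is that the primary result hardly moves. A reader might infer that the 90% CI for SDP/PFS becomes too narrow. It does not: its mean width is 0.99 to 1.01 of the full-data width, even with mandatory use. The plan also sets no acceptance limits for the ratio, so no pass/fail decision is affected. This stands too. The clear understatement is confined to descriptive SDs and geometric CVs.

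Third, the 31% figure belongs to n = 6, the smallest n the rule allows, and not to this trial. The 20% figure at n = 12 would apply to one arm in Period 1 (24/2), but the interim section does not mention outlier testing.

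Fourth, exclusions are visible: data are listed and excluded values documented. That lets a reader see what was dropped, but it does not show the effect on the ratio.

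**Conclusion.** The point holds as a defect in the cut-off. Run on clean log-normal data, the test offers a valid value for exclusion in about 18% of datasets at n = 18 to 24. Passing beyond 3 SD is therefore weak evidence that a value is aberrant. The realised deletion rate per dataset is somewhere between 0 and about 18%.

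If the rule is followed, by-treatment SDs and geometric CVs are about 4% too small on average and 20-25% too small when a value is dropped. CI coverage falls by about 0.5 to 1.5 points.

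The rates in step 2 rest on log-normality alone. The SD and CI effects also assume that the test is run within each treatment, which is an inference because the SAP does not name the dataset. The CI effect further assumes the between-subject range shown and a complete-pairs analysis; the planned mixed model would keep subjects with one remaining value. This merits a change to the SAP, but it does not threaten the primary conclusion.

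**What to change.** In SAP 9.3.1:

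1. In steps 2c to 2e, replace 3 × SD by k(n) × SD, with k(n) = t(n−2; 1 − α/(2n)) × sqrt(n/(n−1)). Here n counts the values before the tested one is removed, and k is recalculated at each repetition. Prespecify α. It is a choice: 5% gives 3.63 and 3.56 at n = 18 and 24, and 1% gives 4.42 and 4.24.
2. Reconcile the introduction to the procedure with step 2e, so that it is clear whether a value outside the range must be excluded or may be.
3. State which set of values the test is run on.
4. For n of six or more, report the SDP/PFS ratio and its 90% CI with and without any excluded value, as the SAP already does for smaller n.

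Testing within-subject differences instead is not a full substitute. A large difference does not show which of the two values is aberrant, and no pairs exist at the Period 1 interim.

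The cost is a few lines of SAP text and one extra set of estimates when a value is excluded. The downside is that a genuinely aberrant value between 3 SD and the new limit stays in the main analysis.
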